This session can be scheduled any time of day. However, the timing of this session will influence when the Day 21 and Day 23 testing appointments are scheduled. Ideally, the subsequent testing sessions would be at the same time of day but can be scheduled up to 3 hours earlier or later than the Baseline session. However, the sessions may go beyond 3 hours as determined by PI/Co-I discretion.

- Remote Check-In(Days 7 and 14). These sessions will be completed remotely via phone or videoconference and will last about 20 minutes. Participants will be asked to:

1. Report their smoking rate (timeline followback; TLFB)
2. Report their medication adherence
3. Report side effects and complete a concomitant medication review
4. Complete measures for mood, smoking urges, withdrawal symptoms, and subjective effects
5. Complete the MADRS, YMRS, Bipolar Disorder Additional Screener, if necessary
6. Review instructions for medication

This visit can be scheduled any time during the day and can be moved by plus or minus 1 day to accommodate for participant's schedule.

- Pre-Quit Testing Day (Day 21). Participants will be asked to bring their study medication to this visit. During this 2-hour visit, participants will complete the same activities they completed at the Baseline Session except that they will complete additional measures of pill count.

- Mandatory 24-H Abstinence Period. On Day 22, participants will receive a telephone call to remind them to begin their practice quit attempt approximately 24 hours before their scheduled 24-H testing session on Day 23. Participants will also be reminded that in order to remain eligible for the study, they must remain abstinent during this 24-hour period.

- 24-H Testing Day (Day 23). The 24-H Testing Day occurs after approximately 24 hours of abstinence from nicotine. The Testing Day Visit takes about 2 hours to complete and is split into two parts. The procedures participants will complete within each part of the Testing Day Visit are as follows:

- 24-H Testing Day Part 1

On Day 23 Part 1, participants will provide:

1. A CO sample to verify abstinence. Mandatory abstinence will be biochemically confirmed by a CO reading of less than or equal to 8 ppm. If the CO reading is not less than 9 ppm, but there is a 50% reduction from the CO collected at the Baseline Visit, this will be considered sufficient and the participant may continue as scheduled. If neither condition is met, but participant reports abstinence, investigator approval will be needed for participant to continue with the session. If a participant smokes (self-reported or biochemically confirmed) during the mandatory abstinence period, they may be withdrawn from the study.
2. A urine sample for a urine drug screen and (if applicable) pregnancy test. If urine drug screen is positive, participants may be withdrawn from the study. Participants believed to have a false-positive result may continue in the study, with investigator approval.
3. Blood pressure (See Blood Pressure Procedures under Screening/covariate measures)
4. Have their blood glucose measured via a handheld glucose monitoring test (see Measures: Screening/Covariates). Subjects who have a low blood glucose level (i.e., less than 70 mg/dl) will be provided a beverage containing at least 15 g carbohydrates (e.g., 4 oz of fruit juice).
5. Report their medication adherence/review pill count*
6. Report side effects and concomitant medication review*
7. Complete questionnaires (mood, smoking urges, attention, and withdrawal symptoms) *

8. MADRS, YMRS, Bipolar Disorder Additional Screener, if necessary*
9. Complete a cognitive task battery (described below)

- 24-H Testing Day Part 2 (Programmed Lapse)

1. Participants will be instructed to smoke one of their own cigarettes in the CIRNA Smoking Laboratory.
2. Following the programmed lapse, participants will complete the assessments of the subjective and rewarding effects of the 'programmed lapse' cigarette (Table 1).

* Some tasks may be completed remotely to reduce the length of in-person visits.

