The objective of this proof-of-concept pilot study is to establish feasibility and generate measures of effect size to support future research to evaluate metformin as a potential smoking cessation aid and whether HIV status moderates these effects.

2. *Primary Outcome Variable(s)*

The primary outcomes are mood and cognitive function following 24h of smoking abstinence.

3. *Secondary Outcome Variable(s)*

Smoking behavior (e.g., cigarettes per day, carbon monoxide) during the 3-week run-up period.

BACKGROUND

Tobacco smoking is the leading cause of preventable death worldwide and presents a major public health burden [1, 2]. In the United States alone, tobacco smoking accounts for over 400,000 deaths per year, yet 17% of adults continue to smoke [3, 4]. Although the ability of smokers to quit has been aided by new medications and counseling, over 50% of smokers relapse in formal treatment programs within the first week following a quit attempt [5-7] and only 5-10% achieve long-term abstinence [8, 9]. In order to identify novel treatments for smoking cessation, a better understanding of the mechanisms by which relapse occurs is necessary. Two plausible behaviors to target are negative affect and cognitive function. Indeed, in the general population nicotine withdrawal produces increases in negative affect [10-12] and disruption of cognitive function [13-16], often within the first 24 h of abstinence [17, 18]. Importantly, withdrawal-related negative affect [19, 20] and cognitive impairment [21, 22] predict relapse.

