We hypothesize that because HIV-infected individuals are more likely to experience mood disturbance [36, 37] and cognitive dysfunction [38, 39], MET (vs. placebo) will attenuate increases in mood disturbance and cognitive dysfunction (verbal and working memory, executive function, and response inhibition) following 24 hours of smoking abstinence among HIV-infected smokers. We will also test whether MET (vs. placebo) reduces smoking behavior (e.g., cigarettes per day, carbon monoxide) during the 3-week drug run-up. Lastly, we will explore whether there is an added benefit to increasing the dose to 1500 mg (vs. 500 mg) without corresponding adverse effects. The proposed study is uniquely positioned to identify a potential new smoking cessation treatment for a population of smokers with high smoking relapse rates.

CHARACTERISTICS OF THE STUDY POPULATION

1. Target Population

Adult, non-treatment seeking smokers (HIV-: n=54; and HIV+: n=30), between the ages of 18-65, reporting consumption of at least 10 cigarettes per day for at least the past 6 months will be the target population for the study. HIV-infected smokers have been diagnosed with HIV/AIDS (identified through the UPENN CFAR Clinical Core, UPHS PennChart reviews and community-based HIV/AIDS organizations and events; see specific criteria below) and HIV-uninfected smokers will have no diagnosis of HIV, either via blood test (see recruitment strategy below) or self-report.

2. Accrual

One hundred and sixty HIV- and ninety HIV+ subjects will be enrolled in order to have 54 HIV- and 30 HIV+ smokers complete all sessions, accounting conservatively for 30% attrition. Participants will first be screened over the phone and then complete an in-person Intake to ensure final eligibility. Enrolled participants will be randomized to one of the three groups: low dose (500 mg), high dose (1500 mg), or placebo.

3. Key Inclusion Criteria

Eligible subjects will be males and females:

1. 18 years of age or older who self-report smoking at least 5 cigarettes (menthol and non-menthol) per day, on average for the past 6 months.
2. **HIV status**
 - a) HIV-infected smokers: diagnosed with HIV infection and exhibiting viral load of less than or equal to 1000 copies/mL and CD4+ counts of greater than or equal to 200 cells/mm³ within 6 months prior to enrollment.
 - b) HIV-uninfected smokers: no diagnosis of HIV, either via blood test or self-report.
3. Must not currently be interested in quitting smoking.

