Final Eligibility is defined as: Liver function test results and GGT liver enzyme levels that are no more than 20% outside the normal, clinical range and serum creatinine levels less than 1.5 mg/dL [males], less than 1.4 mg/dL [females]]. Albumin/Globulin ratios 20% outside of normal range will be evaluated for clinical significance by the Study Physician and eligibility will be determined on a case-by-case basis.

Eligible subjects will confirm the study schedule and be randomized to a medication group. Ineligible subjects may be referred to other studies at our center.

- **Baseline Session (Day 0).** Participants will complete a 1.5-hour Baseline session before starting study medication. The Baseline session must be scheduled at least 2 days after Intake, but no more than 30 days can elapse between Intake and Baseline. At the Baseline session participants will:
 1. Provide a CO sample.
 2. Provide urine specimens for drug and (if applicable) pregnancy tests. Participants who test positive for the urine drug screen may be withdrawn from the study. Participants believed to have a false-positive result may continue in the study, with investigator approval.
 3. Complete a blood pressure measurement (See Blood Pressure Procedures under Screening/covariate measures).
 4. Have their blood glucose measured via a handheld glucose monitoring test (see Measures: Screening/Covariates). Subjects who have a low blood glucose level (i.e., less than 70 mg/dl) will be provided a beverage containing at least 15 g carbohydrates (e.g., 4 oz of fruit juice).
 5. Provide two 10 ml and 2 8.5 ml blood samples (less than 3 tablespoons) for examining biomarkers of neuroinflammation (HIV+ subjects only).
 6. Complete questionnaires (smoking rate, concomitant medication review, withdrawal, smoking urges, mood, subjective effects, and side effects). *
 7. MADRS, YMRS, Bipolar Disorder Additional Screener, if necessary*
 8. Complete cognitive tasks which may include tasks assessing working memory (n-back), verbal learning memory (HVLT-R), cognitive flexibility (color shape task), response inhibition (stop-signal task), and delay discounting.

9. Be given instructions for study medication. Medication may be mailed to the participant or provided at the session.

* Some tasks may be completed remotely to reduce the length of in-person visits.

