Suicidal Behavior and Ideation (C-SSRS). All participants will complete the C-SSRS (Screening Version) with a trained staff member remotely or in-person. The C-SSRS is a structured interview that assesses the suicidal behavior and suicidal ideation in subjects [56, 57]. Occurrence of lifetime suicidal behavior is defined as having answered "yes" to at least 1 of the 4 suicidal behavior sub-categories (actual attempt, interrupted attempt, aborted attempt, and preparatory acts or behavior). Current suicidal ideation is defined as having answered "yes" to at least 1 of the suicidal ideation sub-categories (wish to be dead, non-specific active suicidal thoughts, active suicidal ideation with any methods without intent to act, active suicidal ideation with some intent to act [without specific plan], and active suicidal ideation with specific plan and intent) over the past month.

Carbon Monoxide. Carbon monoxide (CO) measures will be made using a Vitalograph Breath CO Analyzer (McNeil International, Inc., Lenexa, KS). The manufacturer will have calibrated this device within the past year. A new, disposable cardboard mouthpiece will be provided for each participant. The device has a digital screen which reports CO levels in parts per million (ppm). Participants will be asked to provide a CO breath sample by taking a large breath, holding their breath for two seconds, releasing the breath, then taking another deep breath and holding their breath for 10 seconds, as per the recommendations of the American Thoracic Society. Then, when instructed to do so, participants will exhale as forcefully and as long as they are comfortably capable. The largest value displayed is recorded during all CO breath samples. CO breath samples will be collected at each in-person study visit.

Blood Pressure. At the Intake, participants presenting with elevated blood pressure (i.e., systolic blood pressure greater than 159 and/or diastolic blood pressure greater than 99) will have a second blood pressure reading taken after a ten-minute period in which the participants will be instructed to sit comfortably. If, after the second reading, systolic blood pressure remains greater than 159 and/or diastolic remains greater than 99, the participant will be ineligible for the study, unless determined otherwise by the Study PI/Co-I or Study Physician, upon review.

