3.4 Secondary Outcomes

Smoking Rate (TLFB). We will assess the number of cigarettes smoked on each day throughout the study. A standard timeline follow-back (TLFB) method will be used [68], as we have done previously [69] to assess self-reported smoking rate.

Withdrawal Symptoms. The “Minnesota Nicotine Withdrawal Scale - Revised version”(MNWS_R) [70] captures the current state of nicotine withdrawal [71, 72]. The scale assesses eight DSM-IV items of nicotine withdrawal including: dysphoria or depressed mood, insomnia, irritability/frustration/anger, anxiety, decreased heart rate, difficulty concentrating, restlessness, and increased appetite/weight gain. Participants will rate the intensity of their symptoms on the following scale: 0 = none, 1 = slight, 2 = mild, 3 = moderate, 4 = severe and a summary score will be calculated. This will be administered at all study visits (except the Intake). Withdrawal will be assessed using a “past week” time reference for all visits except the 24-H testing visit on Day 23, which will use a 24-h time reference.

Craving. The 10-item brief QSU questionnaire on smoking urges [73] will be used to assess craving for cigarettes during the medication run-up period. The QSU-B contains 2 subscales (anticipation of reward, relief from negative affect). Craving has also been related to long-term cessation outcome in many, but not all, clinical studies [74]. This will be administered at all study visits (except the Intake). Similar to withdrawal symptoms, craving will be assessed using a “past week” time reference for all visits except the 24-H testing visit on Day 23, which will use a 24-h time reference.

Cigarette Ratings and Subjective Effects. The Cigarette Evaluation Scale (CES), developed to assess subjective effects of smoking [75], is an 11-item Likert-format measure. Questions include items for nausea and dizziness, craving relief, and

Table 1. Study Measures

State	Intake	Baseline	Remote Check-In ^b	Pre-Quit Testing	24-H Abstinent	Programmed Lapse
Study Visit Days	-1	0	7, 14	21	23 Part 1	23 Part 2
Screening Variables/Covariates						
Demographics	X					
Nicotine Dependence (FTND/Cigarette Brand)	X					
Smoking/ETOH History	X					
Medical History	X					
Height/Weight*	X	X		X		
Psychiatric/Substance Use Hx (MINI)	X					
Suicidal Ideation/Bx (C-SSRS)	X					
Bipolar Disorder Symptoms (MADRS, YMRS, additional screener) ^a	X	X	X	X	X	
Carbon Monoxide (CO)	X	X		X	X	X
Blood Pressure	X	X		X	X	

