ShIPLEY Institute of Living Scale	X					
Urine Drug Screen	X	X		X	X	
Pregnancy Screen	X	X		X	X	
Depression/Anxiety (HADS)	X	X	X	X	X	
Functional Impairment (PAOFI)	X					
Risk Assessment Battery (HIV+ group only)	X					
BASIS-24	X					
SF-12	X					
Quick Inventory of Depression Symptoms	X					
Liver and Renal Function test	X					
Neuroinflammation (HIV+ group only)		X		X		
Blood Glucose		X		X	X	
Treatment Variables						
Concomitant Medication Review		X	X	X	X	
Medication Side Effects		X	X	X	X	
Pill Count			X	X	X	
Primary Outcomes						
Mood (PANAS)		X	X	X	X (24h)	X (now)
Neurocognitive Test Battery		X		X	X	
Secondary Outcomes						
Cigarette Consumption (TLFB)		X	X	X	X	X
Withdrawal (MNWS-R)		X	X	X	X (24h)	X (now)
Craving (QSU-B)		X	X	X	X (24h)	X (now)
Subjective Effects, Cigarette Ratings (CES, SQ)		X	X	X		X

*Note: Height and weight will be collected at intake visit, weight only will be collected at each subsequent study visit except day 23

^a Only administered if a diagnosis of bipolar disorder is self-reported or revealed via the MINI at intake

^b These visits will be completed remotely via phone or videoconference

enjoyment of airway sensations. The Rose Sensory Questionnaire (SQ), a 9-item Likert-format measure, will be used to assess how much they liked the cigarette smoked and how high in nicotine the cigarettes appeared to be. The questionnaire also includes a diagram of the respiratory tract and asks participants to rate the strength of the cigarette puffs on their tongue, nose, back of mouth and throat, windpipe, and chest. The CES and SQ will be administered at each visit following the Intake.

2. Statistical Analysis

Sample size and analysis. For this analysis we will be estimating summary statistics by group, including means, standard deviations, within-subject correlations, and related confidence intervals. Our sample of 18 per group will yield 95% confidence intervals with limits that fall less than 1/2 SD from the mean. For correlation, the 95% CI length will be no larger than 0.94 if $r=0$, and substantially narrower for $r \neq 0$. Because the goal of this study is to demonstrate feasibility and provide preliminary data, we will not conduct formal hypothesis testing. We will use these measures to estimate interaction effect sizes to plan future research.

3. Confidentiality

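### Carbon monoxide is named as a run-up outcome, but the schedule gives one on-drug reading during usual smoking (Day 21); define the outcome as Day 21 CO adjusted for pre-drug CO

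*Combined protocol and SAP*

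**What the plan says.** The Objectives (item 3, Secondary Outcome Variable(s)) name "Smoking behavior (e.g., cigarettes per day, carbon monoxide) during the 3-week run-up period", and the Protocol Abstract says the same. The last paragraph of the Background makes it a treatment comparison: whether metformin, against placebo, "reduces smoking behavior (e.g., cigarettes per day, carbon monoxide) during the 3-week drug run-up".

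The measurement sections read differently.

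- Section 3.1 describes CO among the screening/covariate measures and states: "CO breath samples will be collected at each in-person study visit".
- Study Visits says of the Day 7 and Day 14 check-ins: "These sessions will be completed remotely via phone or videoconference and will last about 20 minutes". Their task list has six items and CO is not one of them.
- Table 1 puts CO in the Screening Variables/Covariates block, with the Remote Check-In cell blank. The footnote to that column repeats: "These visits will be completed remotely via phone or videoconference".
- Section 3.4 (Secondary Outcomes) covers timeline follow-back (TLFB), withdrawal, craving and cigarette ratings. It does not mention CO.

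The Statistical Analysis section plans group means, standard deviations, within-subject correlations and confidence intervals, with no formal hypothesis tests. It does not name CO, its time point or a reference value.

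**The concern.** The outcome statement covers a three-week period, and a reader would expect CO to describe that period. The schedule supplies one on-drug value near its end. An analyst cannot tell from the text whether CO is an outcome or a covariate, which visit defines it, or whether it is to be reported as a level, a change or an adjusted difference.

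Two features of the plan make this more than a labelling matter. First, the Day 23 abstinence check expects about 24 hours without smoking to bring CO to 8 ppm or less, or to halve it from Baseline. By that logic a Day 21 reading reflects recent smoking, not Days 1 to 20. Second, the high-dose arm steps up after Day 7 and again after Day 14, so CO carries no information on the first two dose steps.

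The pilot exists to produce effect sizes for a larger trial. A CO effect size whose definition is left open is hard to reuse, and an unadjusted Day 21 summary would be less precise than the scheduled data allow.

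**Working it through.** **Count of readings, from Table 1 and Study Visits**

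| Visit | CO planned | State |
|---|---|---|
| Intake | yes | before drug |
| Day 0 | yes | before drug |
| Day 7 | no | on drug, usual smoking |
| Day 14 | no | on drug, usual smoking |
| Day 21 | yes | on drug, usual smoking |
| Day 23 Part 1 | yes | after about 24 h abstinence |
| Day 23 Part 2 | yes | programmed lapse |

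Day 0 is pre-drug because "Participants will complete a 1.5-hour Baseline session before starting study medication". Day 21 includes CO because "participants will complete the same activities they completed at the Baseline Session except that they will complete additional measures of pill count", and the Baseline list opens with a CO sample. The run-up therefore has 0 + 0 + 1 = 1 on-drug reading out of three visits. If Day 21 is held remotely, as the Remote Study Participation paragraph allows, the count is 0.

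**The plan's own precision figure.** For n = 18 per group, the half-width for a mean is t(0.975, 17)/√18 = 0.497 SD. This matches the stated limit of less than 1/2 SD. No figure in the plan is disputed here.

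**Value of the pre-drug readings.** Assume a common variance (set to 1) and a common correlation ρ between any two of Intake, Day 0 and Day 21. The documents give no ρ; 0.5 and 0.7 are used as a range. The residual variance of Day 21 CO under each analysis is:

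- unadjusted: 1
- change from Day 0: 2(1 − ρ)
- adjusted for Day 0: 1 − ρ²
- adjusted for the mean of Intake and Day 0: 1 − 2ρ²/(1 + ρ)

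For the last, the covariance of Day 21 with the mean is ρ and the variance of the mean is (1 + ρ)/2, so R² = 2ρ²/(1 + ρ). That is 0.5/1.5 = 0.333 at ρ = 0.5 and 0.98/1.7 = 0.576 at ρ = 0.7.

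| Analysis | SD at ρ = 0.5 | SD at ρ = 0.7 |
|---|---|---|
| Unadjusted | 1.000 | 1.000 |
| Change from Day 0 | 1.000 | 0.775 |
| Adjusted for Day 0 | 0.866 | 0.714 |
| Adjusted for the two-reading mean | 0.816 | 0.651 |

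CI half-widths scale with these SDs. The reduction from using the two-reading mean is:

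- against unadjusted: 1 − 0.816 = 18%; 1 − 0.651 = 35%
- against change from Day 0: 1 − 0.816/1.000 = 18%; 1 − 0.651/0.775 = 16%
- against Day 0 adjustment alone: 1 − 0.816/0.866 = 6%; 1 − 0.651/0.714 = 9%

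These ratios ignore the small cost of estimating one slope.

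**A different quantity: what Days 7 and 14 would have added.** Averaging three on-drug readings would multiply the SD by √((1 + 2ρ)/3), which is 0.816 at ρ = 0.5 and 0.894 at ρ = 0.7. That is 18% and 11% narrower than a single reading, before any baseline adjustment and for a different target (the run-up average).

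**The case against.** The strongest reply is that nothing promised is missing. The outcome is smoking behavior, with CO given as an example. Section 3.4 records cigarettes for each day by TLFB, Day 21 lies within the run-up, and the documents nowhere promise weekly CO or biochemical validation of TLFB. Much of this stands, and it rules out several stronger conclusions that a reader might draw.

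- *The secondary outcome does not exist.* Not supported. Its main component is recorded daily, and CO has a Day 21 value.
- *The trial cannot say whether CO fell.* Not supported. A Day 0 to Day 21 change by arm can be formed; only the intermediate course is unavailable.
- *The pre-drug readings go unused.* Not supported. Day 0 CO is the reference for the 50% reduction rule on Day 23. What is missing is a stated role in the outcome analysis.
- *The absent Day 7 and Day 14 readings cost up to 35% in precision.* Not supported. That figure is the gain from baseline adjustment against the weakest comparator.
- *No participant has CO on Days 7 or 14.* Not shown. Enrollment was planned from March 2016 and Version 15 is dated August 2020. The documents do not show what earlier versions collected.

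Equal correlations are also a simplification. Intake may precede Day 0 by up to 30 days, and a weaker link between Intake and Day 21 would shrink the gain from adding Intake.

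The reply does not remove the disagreement between the outcome statement, section 3.4 and Table 1, or the lack of any stated CO analysis.

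**Conclusion.** The mismatch is real for the schedule as written in Version 15. CO is named as a run-up outcome, is listed only as a covariate, and has one on-drug, usual-smoking reading. That reading supports a Day 21 comparison or a change from Day 0, not a statement about the course of CO across the three weeks.

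Using the pre-drug readings improves precision at no measurement cost. How much depends on what would otherwise be done: most against an unadjusted Day 21 comparison, least against adjustment for Day 0 alone. The figures rest on an assumed within-person correlation of 0.5 to 0.7, equal for all pairs of readings. The point is worth correcting, but its weight is modest: CO is a secondary measure, cigarettes per day is untouched, and the pilot estimates without testing.

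**What to change.** 1. Define the CO secondary outcome as CO on Day 21. In the Abstract, Objectives and Background, replace the general reference to CO over the run-up with that time point.
2. In Statistical Analysis, state that each metformin-versus-placebo difference in Day 21 CO will be estimated with a 95% CI, adjusted for pre-drug CO. Choose Day 0 or the mean of Intake and Day 0 before analysis. Day 0 alone gives most of the gain if Intake is thought too distant.
3. List CO in section 3.4 and in the Secondary Outcomes block of Table 1.
4. State that smoking between visits rests on TLFB self-report.
5. Say how a missing Day 21 reading is handled, since a remote visit would remove it, and report the number missing by arm.

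The cost is wording in these places and one analysis line. No visit, sample or participant is added. The price is a narrower stated outcome for CO, which matches what the schedule can deliver.

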To ensure a high level of retention and adherence in this trial we will: 1) educate subjects about the benefits of protocol compliance; 2) schedule in-person sessions at convenient times (e.g., evenings); and 3) provide modest financial compensation for session completion and transportation costs.

Referral Bonus Program

Participants who achieve their final study visit (Day 23) will be given the opportunity to receive a small bonus for referring others to the program. If the person who is referred completes the initial eligibility phone screen, regardless of outcome, the study participant will be awarded \$20 per referral, for a maximum of 3 referrals (\$60).

[figure not shown]
STUDY DESIGN

1. Phase

N/A

2. Design

We propose to conduct a randomized, placebo-controlled, parallel arm study with one between-subjects factor of medication (low dose, high dose, placebo). Once eligibility is confirmed after Intake, subjects will attend a clinic visit (day 0) to establish baseline smoking rate, mood, and cognition. Subjects will then be randomized to one of three groups (low dose: 500 mg, high dose: 1500 mg, or placebo) and will complete 4 additional sessions (days 7, 14, 21, 23) to assess side effects, smoking rate, mood, craving, and withdrawal (Figure 1). Cognitive function will also be assessed on days 21 and 23. Subjects will be instructed to refrain from smoking for 24 hours prior to the laboratory session on day 23 (Figure 1). Following FDA guidelines, the dosing regimen for metformin extended release (XR) will be 500 mg q.d for the low dose. For the high dose, the dosing regimen will be: 500 mg q.d (days 1-7); 1000 mg q.d (days 8-14); 1500 mg q.d (days 15-23).

3. Study Duration

Estimated length of time to enroll all subjects and complete the study

Enrollment will start in March 2016. We estimate that we will need to telephone screen 660 smokers to enroll 160 HIV-smokers into the study. We expect a drop-out rate of 30% based on prior experience and expect to have 54 HIV- smokers complete the study. In addition, we will telephone screen 400 HIV+ smokers to enroll 90 and have 30 HIV+ smokers complete the study. We estimate enrolling 4-5 smokers per month.

Length of a subject’s participation time in study

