We estimate it will take a minimum of 4 weeks for a participant to complete the entire study. However, this time period may be longer to accommodate participant schedules or scheduling difficulties between the Intake and baseline visit. Thus, the maximum duration a participant can be in the study is 10 weeks. Additionally, subjects may be contacted after study participation to clarify self-report data collected during their active participation, if necessary for data analysis.

Projected date of completion of the proposed study

We estimate that 54 HIV- and 30 HIV+ smokers will have completed the study by January 2021, and that analyses and reporting will be complete by April 2021.

DRUGS OR DEVICES

Metformin

The study will be performed using metformin, which is currently marketed for the treatment of type 2 diabetes mellitus.

The proposed study follows the typical dosing regimen for metformin for both the low and high dose groups. The dosing regimen for metformin extended release (XR) will be 500 mg q.d for the low dose. For the high dose, the dosing regimen will be: 500 mg q.d (days 1-7); 1000 mg q.d (days 8-14); 1500 mg q.d (days 15-23). This dosing regimen is documented to be safe and well-tolerated in prior clinical studies with no gender or age effects on its pharmacokinetics [51, 52]. Participants will be instructed to take the study medication once daily with their evening meal. Metformin will be purchased and packaged into blister packs by the Investigational Drug Service at the University of Pennsylvania.

An IND exemption has been granted for this study as the results will not be reported to the FDA to support a new drug indication.

Supply, Preparation, Storage, Packaging and Dispensing of Study Medication

Metformin will be purchased and supplied via the University of Pennsylvania Investigational Drug Service (P1377). Matched placebo will be made in-house using sucrose filler in gel capsules. The IDS will store the medication as per the manufacturer guidelines. Specifically, medication will be stored at room temperature (20 – 25 degrees centigrade) and in airtight containers. Metformin and the matching placebo will be packaged in blister packs. IDS will oversee the labeling of all study medication, and will assign each kit, which contains medication for one subject, a unique Pharmacy Randomization Number (PRN).

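### The enrolment counts imply losses of about 66%, not the stated 30%, and no stated step explains the difference

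*Combined protocol and SAP*

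**What the plan says.** **Accrual** (Characteristics of the Study Population, 2). The plan enrols 160 HIV- and 90 HIV+ subjects to "have 54 HIV- and 30 HIV+ smokers complete all sessions, accounting conservatively for 30% attrition". After describing telephone screening and Intake, it continues: "Enrolled participants will be randomized to one of the three groups: low dose (500 mg), high dose (1500 mg), or placebo".

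**Study Duration** (Study Design, 3). For the HIV- group: "We estimate that we will need to telephone screen 660 smokers to enroll 160 HIV-smokers into the study", then "We expect a drop-out rate of 30% based on prior experience and expect to have 54 HIV- smokers complete the study". For the HIV+ group: "we will telephone screen 400 HIV+ smokers to enroll 90 and have 30 HIV+ smokers complete the study". No separate rate is given there for the HIV+ group.

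**Procedures** (Study Procedures, 1). Intake tasks settle final eligibility before a participant is enrolled.

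**Section 4.1** (Data and Safety Monitoring Committee). Enrolment ends once 84 subjects have completed the study.

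The only counts given are telephone screened, enrolled and completed. There is no separate count for people entering Intake.

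**The concern.** The 30% is offered as the reason for enrolling 160 and 90, and it does not produce those numbers. Because the counts appear in two sections, this is not an isolated slip.

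The Overall Objectives include establishing feasibility. The annual Data, Safety and Monitoring Report is to set expected against actual recruitment and to give treatment retention. If 160 and 90 are the randomised numbers, the expected proportion completing is 84/250 = 34%. If the 30% is the loss after randomisation, it is 70%. A later trial planned from this pilot would take a very different number randomised per completer from one reading than from the other. The number of people expected to be exposed to study treatment differs in the same way, 250 against 121.

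**Working it through.** **Inputs.** Enrolled: 160 HIV-, 90 HIV+ (Accrual, Study Duration). Completers: 54 and 30 (same sections). Attrition: 30% (same sections). Telephone screened: 660 and 400 (Study Duration).

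**1. Can the plan's own figure be reproduced?** The usual inflation is N = completers / (1 - d), with d = 0.30.
- HIV-: 54 / 0.70 = 77.1, so 78. Stated: 160.
- HIV+: 30 / 0.70 = 42.9, so 43. Stated: 90.
- Total: 78 + 43 = 121. Stated: 250, which is 129 more.

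Other constructions:

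| Construction | HIV- | HIV+ |
|---|---|---|
| Stated | 160 | 90 |
| completers × 1.30 | 71 | 39 |
| 30% read as the proportion retained (completers / 0.30) | 180 | 100 |
| two successive 30% losses (completers / 0.49) | 110 | 61 |
| three successive 30% losses (completers / 0.343) | 157 | 87 |

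Only the last comes close, and nothing in the protocol describes attrition of 30% at each of three stages.

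**2. Loss implied by the stated counts**, 1 - completers / enrolled.
- HIV-: 1 - 54/160 = 66.3%
- HIV+: 1 - 30/90 = 66.7%
- Overall: 1 - 84/250 = 66.4%

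**3. Completers if 30% were lost from the stated enrolment.** 0.70 × 160 = 112 and 0.70 × 90 = 63, that is 175 rather than 84.

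**4. Do telephone-screen losses explain it?** No. They come before the enrolled count: 1 - 160/660 = 75.8% and 1 - 90/400 = 77.5%.

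**5. What would make the totals agree?** Suppose 160 and 90 enter Intake and the 30% applies after randomisation. The loss before randomisation would have to be 1 - 78/160 = 51.3% (HIV-), 1 - 43/90 = 52.2% (HIV+) and 1 - 121/250 = 51.6% overall. These values are solved backwards from the totals. They are not estimates, and the documents state no such loss.

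**6. Does the text allow that reading?** Procedures puts Intake before enrolment, and Accrual says that enrolled participants are randomised. Taken literally, 160 and 90 are the numbers randomised, and the 30% then has to cover the whole fall to 54 and 30.

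**The case against.** The strongest defence is that 'enrolled' means consented. Consent is the first Intake task. Intake then applies drug screening, psychiatric interviews, a physical examination, and liver and creatinine limits, so a large loss before randomisation is plausible. Study Duration does not say outright that the 30% is taken from the 160. There is also some evidence that 250 is an intended figure: each count has its own telephone-screen number, and with "Enrollment will start in March 2016" and completion projected for January 2021 (about 58 months), 250 / 58 = 4.3 per month fits "We estimate enrolling 4-5 smokers per month". That check is rough, since the window runs to completion rather than to the last enrolment. All this makes the Intake reading credible as the sponsor's intention. It does not make it what the protocol says, because Accrual and Procedures use the word the other way and the required loss appears nowhere.

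It is also fair to say that Version 15 is dated August 2020, close to the projected completion, so a revised forecast has limited value for recruitment. The definition of 'enrolled' still matters for reporting.

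A reader might infer more than the documents support:
- **That two thirds of those randomised are expected to be lost, with selection bias to match.** This follows only if 66% is the true expectation, which is not established.
- **That no count at randomisation is given.** Read literally, Accrual makes 160 and 90 that count. What is missing is a separate count that would reconcile the figures.
- **That the pilot has no feasibility benchmark.** Screened, enrolled and completed targets exist by HIV status, and enrolment stops on completers.
- **That other mismatches cause this one.** The point of randomisation and the monthly accrual rate are also stated inconsistently, but settling either would leave 160 to 54 and 90 to 30 just as far from 30%.

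**Conclusion.** The inconsistency is real and should be corrected. The stated counts imply losses of 66.3% and 66.7% against a stated 30%. At 30% the completer targets need 121 enrolled, not 250. This is arithmetic on the plan's own numbers and needs no outside assumption, except that 30% is one overall loss between enrolment and completion, as the wording indicates.

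The documents do not settle whether a count, the rate or the meaning of 'enrolled' is at fault. The 84-completer target in section 4.1 is unaffected, and so is the precision statement for 18 per group in Statistical Analysis. The effect is confined to the expected attrition, the number randomised and exposed, and the expected recruitment and retention figures.

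**What to change.** Define 'enrolled' and name the step to which the 30% applies. Then restate the expected numbers by HIV status at each stage: telephone screened, entered Intake, randomised, completed. One of two versions should follow.

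- **If 160 and 90 are people entering Intake:** label them so, give 78 + 43 = 121 randomised at 30% attrition after randomisation, and state the expected loss before randomisation from the sponsor's own experience. The back-solved 51-52% should not be used as that estimate.
- **If 160 and 90 are randomised numbers:** restate the expected attrition as about 66%.

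Two separate, minor points can be corrected in the same amendment:

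- **Point of randomisation.** Design and Procedures place it after the day 0 visit, while the Final Eligibility Phone Call paragraph places it before Baseline. Up to 30 days may separate Intake and Baseline, and a positive Baseline drug screen may lead to withdrawal, so retention needs one stated starting point.
- **Monthly accrual.** It is 4-5 in Study Duration and 3-4 in section 4.1. Give one rate and the stage it counts.

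The cost is protocol wording and a short recruitment flow. No extra participants or procedures are needed.
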